8.5.4 Other Assessments

Local tolerability assessment

Local tolerability of the injection site will be assessed by clinical evaluation by the investigator or delegate of the following parameters:

- Erythema/redness
- Induration/swelling
- Ecchymosis/bruising
- Pain

The presence of erythema, induration and ecchymosis will be evaluated visually. If the size of any of these abnormalities is above 2.5 cm, the exact size of the lesion must also be measured.

The lesion size will be estimated and recorded as the largest diameter of the best fitted ellipsoidal form. Lesions will be graded as described below and recorded in the eCRF:

Mild lesion: 2.5-5 cm

Moderate lesion: 5.1-10 cm

Severe lesion: >10 cm

Discontinuation and completion 9

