The risks associated with s.c. administration includes injection site reactions and hypersensitivity. Results of the SAD study in HVs with s.c. MIJ821 indicate that local tolerability of MIJ821 administered via the s.c. route was good. Mild pain, pruritus and bruising occurred in each dose group. All events were mild and self limiting.

In general, hypersensitivity can manifest with itching, flushing, headache, nausea/vomiting, hypotension, urticaria, bronchospasm, or angioedema. In the event of a hypersensitivity reaction, assess and treat for anaphylaxis, if indicated, and initiate supportive care as per local practice. Fluids, vasopressors, corticosteroids, antihistamines, bronchodilators, and oxygen should be at hand.

Potential MIJ821-related risks to the fetus and prevention of pregnancies:

MIJ821 is not genotoxic. Pivotal EFD studies in rats and rabbits showed that MIJ821 is not teratogenic. While MIJ821 was well tolerated in rats in the absence of maternal or embryofetal toxicity, treatment of pregnant rabbits with MIJ821 was associated with embryo lethality at maternally toxic dose levels. The NOAEL for maternal and fetal effects was established at 3 mg/kg/day which is associated with an AUC-based safety margin of 5.9-fold when compared with 0.16 mg/kg human dose.

Taking the study treatment may involve unknown risks to the fetus if pregnancy were to occur during the study.

Women of child-bearing potential and sexually active males must be informed that taking the study treatment may involve unknown risks to the fetus if pregnancy were to occur during the

Page 37 of 104
Protocol No. CMIJ821B12201

study, and agree that in order to participate in the study they must adhere to the contraception requirements outlined in the exclusion criteria. If there is any question that the participant will not reliably comply, they should not be entered or continue in the study.

COVID-19 related risks

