Guidance issued by local regulatory bodies on this aspect prevail and must be implemented and appropriately documented (e.g. the presence of an impartial witness, sign/dating separate ICFs by trial participant and person obtaining informed consent, etc.).

8 Visit schedule and assessments

The Assessment Schedule (Table 8-1) lists all study assessments and when they are performed. All data obtained from these assessments must be supported in the participant's source documentation.

Participants should attend on-site study visits as outlined in the assessment schedule (Table 8-1) or as close to the designated day/time as possible. This is especially important for the Day 2 visit at which primary efficacy assessments are performed. Missed or rescheduled visits should not lead to automatic discontinuation. In addition, the participant will be contacted by phone in between on-site visits (Follow-up call) to collect information about adverse events and concomitant medications. In case follow-up calls have to be shifted by +/- 3 days, follow-up calls can be replaced by on-site visits in accordance to the original visit schedule.

In case a visit is performed outside the schedule, subsequent visits shall be performed in accordance to the original visit schedule. In addition to the scheduled visits, participants may have unscheduled visits for safety monitoring purposes at the discretion of the Investigator. Data collected during unscheduled visits will be recorded in the unscheduled visit CRFs.

Participants who discontinue from the study or withdraw their consent/oppose the use of their data/biological samples should be scheduled for a final evaluation visit if they agree, as soon as possible, at which time all of the assessments listed for the final visit will be performed. At this final visit, the adverse events and concomitant medications not previously reported must be recorded on the CRF.

The "X" in the table denotes the assessments to be recorded in the clinical database or received electronically from a vendor. The "S" in the table denotes the assessments that are only in the participant's source documentation and do not need to be recorded in the clinical database.

Every effort will be made to draw the PK samples at the protocol specified timepoints. Other assessments (e.g., ECG, vital signs, etc.) will be taken prior to the PK sample.

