As per Section 4.6, during a Public Health emergency as declared by Local or Regional authorities i.e. pandemic, epidemic or natural disaster that limits or prevents on-site study visits, alternative methods of providing continuing care may be implemented by Novartis as the situation dictates. If permitted/approved by local or Regional Health Authorities and Ethics Committees as appropriate and depending on operational capabilities, phone calls, virtual contacts (e.g. tele consult) or visits by site staff/ home nursing staff to the participant's home, can replace on-site study visits, for the duration of the disruption until it is safe for the participant to visit the site again.

Table 8-1 Assessment Schedule

Table 0-1	A336331	1101		JOHICO	iuic															
Period	Screening					Trea	tment						Follow-up							
Visit Name	Screening									Follow- up call	Follow- up visit	Follow- up call	Follow- up visit	Follow- up call		Follow- up call				
Visit Numbers ¹	1					20						40	50	60	70	80	90	100	110	120
Days	-28 to -1					1						2	4	8	11	15	18	22	25	29
Time (post-dose)	-	- 1h	0h	0.17h	0.33h	0.5h	0.75h	1h	1.5h	2h	4h	24h	•	-	-	-	-	-	-	-
Informed consent	Х																			
Inclusion / Exclusion criteria	Х	Х																		
Medical history/current medical conditions	×																			
SCID-5	S ³																			
MGH-ATRQ	S ³																			
Alcohol Test and Drug Screen	S ³	S ³																		
Pregnancy and assessments of fertility ⁴	Х	X ⁵																		х
Demography	Х																			
Body Height	Х																			
Body Weight	Х	Х																		Х
Physical Examination	S ³																			S ³

Period	Screening					Trea	tment									Follo	w-up			
Visit Name	Screening									Follow- up call	Follow- up visit	Follow- up call	Follow- up visit	Follow- up call	Follow- up visit	Follow- up call				
Visit Numbers ¹	1					20						40	50	60	70	80	90	100	110	120
Days	-28 to -1					1						2	4	8	11	15	18	22	25	29
Time (post-dose)	-	- 1h	0h	0.17h	0.33h	0.5h	0.75h	1h	1.5h	2h	4h	24h	-	-	-	-	-	-	-	-
Body Temperature	Х	X										Х								Х
Blood Pressure and Pulse Rate	Х	X ⁶				Х			Х		X	Х		X		Х		Х		Х
Respiratory rate ³	S	ഗ				S			S		S	S		S		S		S		S
Oxygen Saturation						S ^{3,7}	,													
Electrocardiogram (ECG)	Х	X ⁶				Х			Х		X	Х								Х
CADSS		Χ				Х			Х		Χ	Χ		Х		X		X		Х
MOAA/S		Χ				Х			Х		Χ	Χ		Х		Х		Х		X
Memory Assessment Questions ¹³						S					S	s								
C-SSRS	Χ	Х									Х	Х		Х		Х		Х		Χ
Local tolerability assessment						S					S	s								

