Hematology	X ¹¹	Χ										Х								Χ
Clinical Chemistry	X ¹¹	Χ										Χ								Χ
Coagulation Panel	X ¹¹	X										Х								Х
Urinalysis	X ¹¹	Х										Χ								Х
PK blood collection ¹²			X8	Х	Х	Х	Х	х	Х	Х	X	X ⁹								

Pariod Carooning	Trootmo
Amended Clinical Trial Proto	ocol (Version No. 02, Clean)

Period	Screening					Trea	tment						Follow-up							
Visit Name	Screening									Follow- up call	Follow- up visit	Follow- up call	Follow- up visit	Follow- up call	Follow- up visit	Follow- up call				
Visit Numbers ¹	1		20 40							50	60	70	80	90	100	110	120			
Days	-28 to -1					1						2	4	8	11	15	18	22	25	29
Time (post-dose)	ı	- 1h	0h	0.17h	0.33h	0.5h	0.75h	1h	1.5h	2h	4h	24h	-	-	-	-	-	-	-	-
Randomization		Х																		
Dose administration			Х																	
MADRS	Х	Χ									Χ	Χ		Х		Х		Χ		Х
Concomitant therapies	Х	Х										Х	Х	Х	Х	Х	Х	Х	Х	Х
Adverse Events	Х	Χ	Х		Х		Х			Х	Χ	Χ	Х	Х	Х	Х	Х	Х	Х	Х
Study completion information																				Х
Safety follow-up call													Х		Х		Х		Х	

X Assessment to be recorded in the clinical database or received electronically from a vendor

1 Visit structure given for internal programming purpose only

2 Optional for participant

3 S = assessment to be recorded on source documentation only and will not be entered into the eCRF. If drug screen result is positive but does not meet DSM-5 criteria for substance use

- ⁴ Additional pregnancy testing may be performed at each visit to meet local requirements. Serum pregnancy test to be performed, unless specified otherwise.
- ⁵ Urine pregnancy test. Dosing can proceed only if result is negative.
- ⁶ Dosing can proceed if the results are deemed satisfactory by the Investigator.
- ⁷ Every 15 minutes from pre-dose to 4 hours post-dose
- ⁸ Pre-dose
- ⁹ Approximately 24 hours after the injection

disorder, the subject can be randomized.

- ¹¹ All screening laboratory results must be obtained before randomization to ensure participants eligibility
- ¹² In case of unscheduled visits for safety monitoring purposes during the time period from 4 hours to 24 hours after injection, unscheduled PK samples may be collected if operationally feasible.
- ¹³ The outcome of this assessment will only be captured in the eCRF if amnesia is considered as an AE

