8.4.4.3 Memory Assessment using orientation questions

Memory gaps/amnesia are AEs of Special Interest (AESI). Memory Assessment using orientation questions will be assessed by qualified personnel according to Table 8-1.

Orientation questions will be asked to assess presence or absence of amnesia, as well as any distress for the participant, at defined intervals. The outcome of this assessment will only be captured in the eCRF if amnesia is assessed as an AE. In that case, the onset and resolution of amnesia should be identified as precisely as possible and these data will be recorded in the eCRF. While definite amnesia must be reported as an AE in the eCRF, possible mild amnesia may or may not be reported as an AE based on investigator judgment.

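### The scheduled local tolerability check does not ask about pruritus, a reaction already reported with s.c. dosing, and its source-only coding in Table 8-1 conflicts with Section 8.5.4

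*Protocol*

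**What the plan says.** **The check.** Protocol Section 8.5.4: "Local tolerability of the injection site will be assessed by clinical evaluation by the investigator or delegate of the following parameters". Four parameters follow: erythema/redness, induration/swelling, ecchymosis/bruising and pain. The three visible signs are inspected, and measured if larger than 2.5 cm. On size grades the section says: "Lesions will be graded as described below and recorded in the eCRF". The grades run from mild (2.5 to 5 cm) to severe (over 10 cm). No scale is given for pain, and pruritus does not appear.

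**Prior s.c. experience.** Section 4.5, on the single ascending dose study in healthy volunteers: "Mild pain, pruritus and bruising occurred in each dose group". It adds that every event was mild and self-limiting. Section 1.1.3 describes the data available from that study as preliminary and blinded.

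**Schedule and coding.** In Table 8-1 the row "Local tolerability assessment" carries the code 'S' at 0.5, 4 and 24 hours. Section 8 explains that 'S' assessments are kept only in the participant's "source documentation and do not need to be recorded in the clinical database". Footnote 3 of the table is firmer: "S = assessment to be recorded on source documentation only and will not be entered into the eCRF".

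**Endpoint and analysis.** Local tolerability results are listed under the secondary safety objective in Protocol Table 2-1 and SAP Table 1-1. The visible SAP safety sections (2.7.1 to 2.7.4.6) and Protocol Section 12.5.2 contain no summary of the check.

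**The concern.** There are two issues, and they are separate.

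The first is uneven ascertainment. Pain and bruising are looked for in every participant at three fixed times. Pruritus was reported in the same earlier dose groups, but it has no prompt. Section 3 describes the check as visual inspection, which cannot detect itch. A by-arm comparison of local reactions would therefore rest on prompted data for two of them and unprompted data for the third.

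The second is a conflict over where the data go. One part of the protocol keeps the check out of the eCRF, and another tells sites to put lesion grades into it. If sites follow the table, a component of a secondary endpoint is missing from the database. If they follow 8.5.4, the table is wrong. Practice may then differ between the 20 to 25 centres.

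This matters because the trial is meant to inform dose selection for later studies and has a concurrent saline control, so it is a natural place to compare local symptoms by dose.

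**Working it through.** There is no plan figure to reproduce. The check is a cross-reading with a few counts.

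**1. Reported reactions against prompted parameters**

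| Reaction in each earlier s.c. dose group (4.5) | On the 8.5.4 list? | Grade defined in 8.5.4? |
|---|---|---|
| Bruising | Yes | Yes, by diameter from 2.5 cm |
| Pain | Yes | No |
| Pruritus | No | No |

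Two of the three are prompted and one is not. Of the four listed parameters, three have a size grade and pain has none.

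**2. Routes by which a symptom can reach the database**

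Section 10.1.1 allows adverse events to be found by non-directive questioning, by volunteered report, or through examinations and other assessments. A recorded event carries a mild, moderate or severe grade.

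- Pain elicited at the check qualifies as found through another assessment, so it has a graded route.
- Pruritus is not elicited at the check. It depends on questioning that does not mention it, on the participant raising it, or on an incidental finding.

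From 0 hours onward, Table 8-1 schedules adverse event collection at 0, 0.33, 0.75, 2, 4 and 24 hours (6 contacts) and on Days 4, 8, 11, 15, 18, 22, 25 and 29 (8 contacts): 6 + 8 = 14. None is specific to itch.

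**3. The coding conflict**

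| Source | Instruction on the check |
|---|---|
| Table 8-1 with footnote 3 | Source documents only, nothing in the eCRF |
| Section 8.5.4 | Lesion grades go into the eCRF |
| Table 2-1 and SAP Table 1-1 | Results belong to the secondary safety endpoint |

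The first row cannot be reconciled with the second, and it fits poorly with the third.

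**4. What this trial adds**

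Earlier s.c. data (Section 1.1.3): three cohorts of eight, randomized 3:1, give 8 × 3/4 = 6 active per cohort, so 3 × 6 = 18 active and 3 × 2 = 6 placebo. This trial: 14 per arm gives 3 × 14 = 42 active and 14 placebo.

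**5. Burden of the change**

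- Added pruritus questions: 3 checks × 56 participants = 168.
- Graded entries if pain and pruritus are both recorded at each check: 2 × 3 × 56 = 336.

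The documents give no count of pruritus cases, so no incidence or number of missed cases can be derived.

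**The case against.** The strongest reply is that adverse event collection already covers local symptoms. Participants are observed continuously for 30 minutes, stay at least 4 hours, and are asked about symptoms repeatedly. Section 4.5 also lists itching among the manifestations of hypersensitivity, so staff are alerted to it. The evidence on pruritus is thin: the data are preliminary and blinded, the cohorts included placebo, nothing attributes the itch to MIJ821, and the documents do not say how it was elicited. For mild events outside the list of adverse events of special interest (Section 10.2.5), non-directive elicitation is a defensible choice.

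Most of this stands, and it rules out several stronger readings that a reader might infer:

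- **That pain findings have no way into the database.** They do. Section 10.1.1 already provides for recording and grading them as adverse events.
- **That the 'S' code withholds pain or pruritus grades.** Section 8.5.4 defines no grade for either, so the code has nothing to withhold. The conflict created by the code concerns lesion grades.
- **That the memory questions show local symptoms lack a rule.** Those questions are also coded 'S', and footnote 13 says: "The outcome of this assessment will only be captured in the eCRF if amnesia is considered as an AE". Section 8.4.4.3 adds that "definite amnesia must be reported as an AE in the eCRF", but the same sentence leaves possible mild amnesia to the investigator's judgement. It does not show that local symptoms fall outside the general rule in 10.1.1.
- **That pruritus will go unrecorded.** Itch that a participant mentions is recorded and graded like any other event. Only the dedicated prompt is absent.

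The reply does not remove the unequal prompting of reactions reported side by side in Section 4.5. It also leaves the contradiction between Table 8-1 and Section 8.5.4 untouched.

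**Conclusion.** The point holds as a low-priority improvement with two parts. The check omits one of three local reactions already reported with s.c. dosing, so ascertainment is uneven. The source-only coding contradicts the instruction to enter lesion grades in the eCRF and sits badly with the endpoint status of the results.

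The practical effect is modest. The earlier events were all mild and self-limiting, frequent adverse event questioning remains as a backstop, and nothing touches the sample size, power, alpha or primary endpoint.

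The conclusion assumes that the column positions in Table 8-1 have been read correctly (0.5, 4 and 24 hours). The absence of a SAP summary is claimed only for the visible safety sections. Neither part requires pruritus to be caused by the drug: the case for prompting is that the reactions should be ascertained alike in all arms.

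**What to change.** **Protocol 8.5.4.** Add pruritus to the list, and state that pain and pruritus are asked about directly at 0.5, 4 and 24 hours. Record each as absent, mild, moderate or severe, using the severity definitions in Section 10.1.1.

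**Table 8-1.** Change the local tolerability row from 'S' to 'X', so that lesion grades and the two symptom grades all enter the eCRF. This also removes the conflict with 8.5.4.

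**SAP 2.7.4.** Add one summary of lesion, pain and pruritus grades by arm and time point.

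**Cost.** A short wording change, one table row, two symptom fields per check and one SAP table. Staff, visits and time points stay the same. Prompted questioning will raise the number of mild events in all blinded arms, including placebo, so rates will not compare directly with studies that did not prompt. The comparison between arms within this trial is made on equal terms.

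If only one change is accepted, adding pruritus to the list gives most of the benefit for ascertainment: a positive answer can then be recorded under 10.1.1 and would appear in the planned tables by preferred term and maximum severity. The 'S' code would still need to be reconciled with 8.5.4.

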9.1 Discontinuation from study treatment and from study

9.1.1 **Discontinuation from study treatment**

This is a single dose study, therefore treatment discontinuation for the individual participant is not applicable.

9.1.2 **Discontinuation from study**

Discontinuation from study is when the participant permanently stops further protocol-required assessments or follow-up.

If the participant agrees, a final evaluation at the time of the participant's study discontinuation should be made as detailed in the assessment table (refer to Section 8).

9.1.3 Lost to follow-up

For participants whose status is unclear because they fail to appear for study visits without stating an intention to discontinue from study or withdraw consent/oppose to the use of their data/biological samples, the investigator must show "due diligence" by documenting in the source documents steps taken to contact the participant, e.g. dates of telephone calls, registered letters, etc. A participant should not be considered as lost to follow-up until due diligence has been completed or until the end of the study.

9.2 Withdrawal of informed consent/Opposition to use data/biological samples

Withdrawal of consent/opposition to use of data and/or biological samples occurs in countries where the legal justification to collect and process the data is consent and when a participant:

Explicitly requests to stop use of their data

and

No longer wishes to receive study treatment

and

Does not want any further visits or assessments (including further study-related contacts)

This request should be as per local regulations (e.g. in writing) and recorded in the source documentation.

Withdrawal of consent impacts ability to further contact the participant, collect follow-up data (e.g. to respond to data queries) and potentially other country-specific restrictions. It is therefore very important to ensure accurate recording of withdrawal vs. discontinuation based on the protocol definitions of these terms.

In this situation, the Investigator should make a reasonable effort (e.g. telephone, e-mail, letter) to understand the primary reason for the participant's decision to withdraw their consent/exercise data privacy rights and record this information. The Investigator shall clearly document if the participant has withdrawn his/her consent for the use of data in addition to a study discontinuation.

No further assessments must conducted, and the data that would have been collected at subsequent visits will be considered missing.

Further attempts to contact the participant are not allowed unless safety findings require communicating or follow-up.

If the participant agrees, a final evaluation at the time of the participant's withdrawal of consent/exercise data privacy rights should be made.

Further details on withdrawal of consent or the exercise of participants' data privacy rights are included in the corresponding informed consent form.

9.3 Study stopping rules

Not applicable.

9.4 Study completion and post-study treatment

Study completion is defined as when the last participant finishes their End of Study visit and any repeat assessments associated with this visit have been documented and followed-up appropriately by the Investigator or, in the event of an early study termination decision, the date of that decision.

The information collected is kept as source documentation. All SAEs reported during this time period must be reported as described in Section 10.1.3. Documentation of attempts to contact the participant should be recorded in the source documentation.

9.5 Early study termination by the sponsor

The study can be terminated by Novartis at any time.

Reasons for early termination:

- Unexpected, significant, or unacceptable safety risk to participants enrolled in the study
- Decision based on recommendations from applicable board(s) after review of safety and efficacy data
- Discontinuation of study drug development

In taking the decision to terminate, Novartis will always consider participant welfare and safety. Should early termination be necessary, participants must be seen as soon as possible and treated as a participant who discontinued from study treatment. The investigator may be informed of

additional procedures to be followed in order to ensure that adequate consideration is given to the protection of the participant's interests. The investigator or sponsor depending on local regulation will be responsible for informing IRBs/IECs of the early termination of the trial.

10 Safety monitoring, reporting and committees

